6.4.1.2 Key Secondary Efficacy Endpoint and Estimand

The key secondary efficacy endpoint is:

• OS, defined as the duration from the date of randomization to the date of death due to any cause. OS will be calculated in months as:

OS (months) = (date of death - date of randomization + 1) / 30.4375.

	Estimand Category					
		Population		Intercurrent	Populatio	
		(Based on	Variable/	Event;	n Level	
Objective	Treatment	ITT)	Endpoint	Strategy	Summary	
OS: To demonstrate the superiority of tamibaroten e plus azacitidine compared to placebo plus azacitidine in OS in RARA- positive newly diagnosed HR-MDS patients	Tamibaroten e plus azacitidine versus placebo plus azacitidine	RARA- positive patients with newly diagnosed HR-MDS according to the WHO classificatio n, classified by the IPSS- R risk category as intermediate, high, or very high risk	OS, defined as the time from the date of randomizatio n to date of death from any cause	Treatment discontinuatio n; Treatment policy Initiation of HSCT or other subsequent anticancer therapy; Treatment policy	Kaplan- Meier estimate of OS and hazard ratio	

Table 4Key Secondary Estimand

Abbreviations: HR-MDS = higher-risk myelodysplastic syndrome; HSCT = hematopoietic stem cell transplantation; IPSS-R = Revised International Prognostic Scoring System; ITT = Intent-to-Treat; OS = overall survival; RARA = retinoic acid receptor alpha; WHO = World Health Organization

6.4.1.3 Secondary Efficacy Endpoints and Estimands

The secondary efficacy endpoints are:

• TI, defined as a period of at least 56 days with no red blood cell (RBC) or platelet transfusion since the date of randomization to the last dose of study drug + 30 days, the initiation of post-treatment therapy, or death, whichever occurs first. TI rate is calculated as:

TI rate (%) = number of participants who achieve TI / number of participants in the mITT analysis set \times 100. The denominator is the mITT population in each treatment group.

• Overall response, defined as achieving CR, partial remission (PR), marrow CR (mCR), or subcategories of hematologic improvement (HI), as determined by the investigator per the modified IWG MDS criteria (Cheson 2006). ORR will be calculated as:

ORR (%) = number of overall responders / number of participants in the mITT analysis set \times 100. The denominator is the mITT population in each treatment group.

Overall response may also be analyzed in line with the updated IWG response criteria (Zeidan 2023).

• DOCR, defined as the duration from the date of first documented evidence of CR to the date of documented relapse of disease or disease progression, as determined by the investigator per the modified IWG MDS criteria (Cheson 2006), or death due to any cause, whichever occurs first. Among CR responders, DOCR will be calculated in months as:

DOCR (months) = (first date of documented relapse of disease, disease progression, or death due to any cause - date of first documented evidence of <math>CR + 1) / 30.4375.

• Duration of overall response, defined as the duration from the date of first documented evidence of CR, PR, mCR, or HI, to the date of documented disease progression or relapse of disease, as determined by the investigator per the modified IWG MDS criteria (Cheson 2006), or death due to any cause, whichever occurs first. Among overall responders, duration of overall response will be calculated in months as:

Duration of overall response (months) = (first date of documented disease progression, relapse of disease, or death due to any cause - date of first documented evidence of CR, PR, mCR, or HI + 1) / 30.4375.

• Time to CR, defined as the duration from the date of randomization to the date of the first documented evidence of CR as determined by the investigator per the modified IWG MDS criteria (Cheson 2006). Among CR responders, this endpoint will be calculated as:

Time to CR (months) = (date of the first documented evidence of CR – date of randomization + 1) / 30.4375.

• Time to initial response, defined as the duration from the date of randomization to the date of the first documented evidence of CR, PR, mCR, or HI as determined by the

investigator per the modified IWG MDS criteria (Cheson 2006). Among overall responders, this endpoint will be calculated as:

Time to Initial Response (months) = (date of the first documented evidence of CR/PR/mCR/HI – date of randomization + 1) / 30.4375.

• EFS, defined as the time from the date of randomization to the date of transformation to AML or death due to any cause, whichever occurs first. EFS will be calculated in months as:

EFS (months) = (date of transformation to AML or death due to any cause - date of randomization + 1) / 30.4375.

• Change in HRQOL as measured by the European Organization for Research and Treatment of Cancer Quality of Life Core Questionnaire 30 (EORTC QLQ-30) and EuroQol 5 dimensions (EQ-5D-5L).

Table 5Secondary Estimands

	Estimand Category				
				Intercurrent Event;	Population Level
Secondary Objectives	Treatment	Population	Variable/Endpoint	Strategy	Summary
TI: To demonstrate the	Tamibarotene plus	RARA-positive	TI, defined as a period	Treatment	• TI rate by treatment
superiority of	azacıtıdıne versus	participants with newly	of at least 56 days with	discontinuation;	arm
tamibarotene plus	placebo plus azacitidine	diagnosed HR-MDS	no RBC or platelet	Treatment policy	
to placebo plus		according to the wHO	date of randomization		
azacitidine in TI		by the IPSS-R risk	to the last dose of study	Participants who die.	
		category as	drug $+30$ days, the	withdraw consent, or	
		intermediate, high, or	initiation of post-	start a new anticancer	
		very high risk in mITT	treatment therapy, or	therapy before	
			death, whichever occurs	achieving a response;	
			first	Composite strategy	
Overall Response: To	Tamibarotene plus	RARA-positive	Overall response,	Treatment	• ORR by treatment
demonstrate the	azacitidine versus	participants with newly	defined as achieving	discontinuation;	arm
superiority of	placebo plus azacitidine	diagnosed HR-MDS	CR, PR, mCR, or HI as	Treatment policy	
tamibarotene plus		according to the WHO	determined by the		
azacitidine compared		classification, classified	investigator per the		
to placebo plus		by the IPSS-R risk	modified IWG MDS	Participants who die,	
azacıtıdıne in overall		category as	criteria (Cheson 2006)	withdraw consent, or	
response		intermediate, high, or		start a new anticancer	
		very high risk and who		therapy before	
		are responders (CR PR,		achieving a response;	
		mCR, or HI) in mITT		Composite strategy	

Version 4.0

	Estimand Category					
				Intercurrent Event;	Population Level	
Secondary Objectives	Treatment	Population	Variable/Endpoint	Strategy	Summary	
DOCR (CR achieved	Tamibarotene plus	RARA-positive	DOCR, defined as the	Treatment	Kaplan-Meier	
by Cycle 7 Day 1): To	azacitidine and placebo	participants with newly	duration from the date	discontinuation and	estimate of DOCR	
characterize the DOCR	plus azacitidine	diagnosed HR-MDS	of first documented	HSCT;		
of tamibarotene plus		according to the WHO	evidence of CR to the	Treatment policy		
azacitidine or placebo		classification, classified	date of documented			
plus azacitidine		by the IPSS-R risk	relapse of disease or			
		category as	disease progression, as	Initiation of subsequent		
		intermediate, high, or	determined by the	anticancer therapy other		
		very high risk and those	investigator per the	than HSC1 prior to		
		Cycle 7 Dev 1 in mITT	modified IWG MDS	Hypothetical strategy		
		Cycle / Day I in mi I I	or death due to any	Trypometical strategy		
			cause whichever			
			occurs first			
Duration of Overall	Tamibarotene plus	RARA-positive	Duration of overall	Treatment	Kaplan-Meier	
Response: To	azacitidine and placebo	participants with newly	response defined as the	discontinuation and	estimate of duration	
characterize the	plus azacitidine	diagnosed HR-MDS	duration from the date	HSCT;	of overall response	
duration of overall		according to the WHO	of first documented	Treatment policy	1	
response (DOR) of		classification, classified	evidence of CR, PR,			
tamibarotene plus		by the IPSS-R risk	mCR, or HI, to the date			
azacitidine or placebo		category as	of documented disease	Initiation of subsequent		
plus azacitidine		intermediate, high, or	progression or relapse	anticancer therapy other		
		very high risk and who	of disease as	than HSCT prior to		
		are responders (CR PR,	determined by the	relapse;		
		mCR, or HI) in mITT	investigator per the	Hypothetical strategy		
			modified IWG MDS			
			criteria (Cheson 2006),			
			or death due to any			
			cause, whichever			
			occurs first			

	Estimand Category				
				Intercurrent Event	Population Level
Secondary Objectives	Treatment	Population	Variable/Endpoint	Strategy	Summary
Time to CR (CR	Tamibarotene plus	RARA-positive	Time to CR. defined as	Treatment	Summary statistics (n.
achieved by Cycle 7	azacitidine and placebo	participants with newly	the duration from the	discontinuation:	mean, median, min,
Day 1): Characterize	plus azacitidine	diagnosed HR-MDS	date of randomization	Treatment policy	max)
the time to CR of	1	according to the WHO	to the date of the first	1 2	,
tamibarotene plus		classification, classified	documented evidence		
azacitidine and placebo		by the IPSS-R risk	of CR as determined by	Participants who die,	
plus azacitidine		category as	the investigator per the	withdraw consent, or	
1		intermediate, high, or	modified IWG MDS	start a new anticancer	
		very high risk and who	criteria (Cheson 2006)	therapy before	
		achieved CR by Cycle 7		achieving a response;	
		Day 1 in mITT		Composite strategy	
Time to Initial	Tamibarotene plus	RARA-positive	Time to initial response,	Treatment	Summary statistics (n,
Response	azacitidine and placebo	participants with newly	defined as the duration	discontinuation;	mean, median, min,
Characterize the time	plus azacitidine	diagnosed HR-MDS	from the date of	Treatment policy	max)
to initial response of		according to the WHO	randomization to the		
tamibarotene plus		classification, classified	date of the first		
azacitidine and placebo		by the IPSS-R risk	documented evidence	Participants who die,	
plus azacitidine		category as	of CR, PR, mCR, or HI	withdraw consent, or	
		intermediate, high, or	as determined by the	start a new anticancer	
		very high risk who are	investigator per the	therapy before	
		responders (CR PR,	modified IWG MDS	achieving a response;	
		mCR, or HI in mITT	criteria (Cheson 2006)	Composite strategy	
EFS: To demonstrate	Tamibarotene plus	RARA-positive	EFS, defined as the	Treatment	Kaplan-Meier estimate
the superiority of	azacitidine versus	participants with newly	time from the date of	discontinuation;	of EFS
tamibarotene plus	placebo plus azacitidine	diagnosed HR-MDS	randomization to the	Treatment policy	
azacıtıdıne compared		according to the WHO	date of transformation		
to placebo plus		classification, classified	to AML or death due to	Luitintian aftigor an	
azacitidine in EFS		by the IPSS-R risk	any cause, whichever	ather subsequent	
		category as	occurs first.	other subsequent	
		intermediate, high, or		Transformer therapy;	
		very high risk in ITT		Treatment policy	

	Estimand Category					
				Intercurrent Event;	Population Level	

CR (achieved at any time): To demonstrate the superiority of tamibarotene plus azacitidine compared to placebo plus azacitidine	Tamibarotene plus azacitidine versus placebo plus azacitidine	RARA-positive participants with newly diagnosed HR-MDS according to the WHO classification, classified by the IPSS-R risk and who achieved CR at any time in mITT	CR as determined by the investigator per the modified IWG MDS criteria (Cheson 2006)	Treatment discontinuation; Treatment policy Participants who die, withdraw consent, or start a new anticancer therapy before achieving a response; Composite strategy	 CR rate by treatment arm Difference in proportion of CR rate between 2 treatment arms 		
DOCR (CR achieved at any time): To characterize the DOCR of tamibarotene plus azacitidine or placebo plus azacitidine	Tamibarotene plus azacitidine and placebo plus azacitidine	RARA-positive participants with newly diagnosed HR-MDS according to the WHO classification, classified by the IPSS-R risk category as intermediate, high, or very high risk and those who achieved CR at any time in mITT	DOCR, defined as the duration from the date of first documented evidence of CR to the date of documented relapse of disease or disease progression, as determined by the investigator per the modified IWG MDS criteria (Cheson 2006), or death due to any cause, whichever occurs first	Treatment discontinuation and HSCT; Treatment policy Initiation of subsequent anticancer therapy other than HSCT prior to relapse; Hypothetical strategy	• Kaplan-Meier estimate of DOCR		

Table 6Supplementary Primary and Secondary Estimands

	Estimand Category					
				Intercurrent Event;	Population Level	
Secondary Objectives	Treatment	Population	Variable/Endpoint	Strategy	Summary	
Time to CR (CR	Tamibarotene plus	RARA-positive	Time to CR, defined as	Treatment	Summary statistics (n,	
achieved at any time):	azacitidine and placebo	participants with newly	the duration from the	discontinuation;	mean, median, min,	
To characterize the	plus azacitidine	diagnosed HR-MDS	date of randomization	Treatment policy	max)	
time to CR of		according to the WHO	to the date of the first			
tamibarotene plus		classification, classified	documented evidence			
azacitidine and placebo		by the IPSS-R risk	of CR as determined by	Participants who die,		
plus azacitidine		category as	the investigator per the	withdraw consent, or		
		intermediate, high, or	modified IWG MDS	start a new anticancer		
		very high risk and who	criteria (Cheson 2006)	therapy before		
		achieved CR at any		achieving a response;		
		time in mITT		Composite strategy		

Abbreviations: CR = complete remission; DOCR = duration of complete remission; HR-MDS = higher-risk myelodysplastic syndrome; HSCT = hematopoietic stem cell transplantation; IPSS-R = Revised International Prognostic Scoring System; IWG = International Working Group; MDS = myelodysplastic syndrome; mITT = Modified Intent-to-Treat; RARA = retinoic acid receptor alpha; WHO = World Health Organization.

Note: CR, DOCR, and time to CR analysis will be based on the analysis set for those who achieved CR at any time in mITT.

6.4.1.4 Exploratory Efficacy Endpoints

The exploratory efficacy endpoints are:

• Cytogenetic CR, defined as participants achieving cytogenetic CR (Cheson 2006), as determined by the investigator. The cytogenetic CR rate will be calculated as:

Cytogenetic CR rate (%) = number of cytogenetic CR responders / mITT participants with baseline cytogenetics abnormality \times 100.

- Molecular response, defined as participants achieving a reduction in variant allele frequency by next-generation sequencing.
- Transfusion requirement, defined as the frequency and amount of blood products (RBC or platelet) received.
- The rate of consolidation with allogeneic HSCT is defined as the proportion of participants who are treated with allogeneic HSCT. This endpoint is calculated as:

Consolidation with allogeneic HSCT rate (%) = number of participants treated with allogeneic HSCT / number of participants in the mITT analysis set \times 100. The denominator is the mITT population in each treatment group.

• Clinical response and genetic mutations and/or gene expression markers at baseline, at the time of response, and loss of response.

Response types (i.e., CR, PR, mCR, etc.) included in the efficacy endpoints are defined in Table 7 and Table 8. A sample of the EORTC QLQ-30 can be found in Appendix 9, and a sample of the EQ-5D-5L can be found in Appendix 10 of the Study SY-1425-301 protocol.

Response Criteria ^a		Peripheral	Blood		BMB (%)	Other
	Hemoglobin	Neutrophils	Platelets	Blasts		
	(g/dL)	per (L)	per (L)	(%)		
CR	≥11	$\geq 1.0 \times 10^9$	$\geq 100 \times 10^9$	0	≤5	Normal maturation of all cell lines, persistent dysplasia will be noted

Table 7IWG Response Criteria for MDS

Syros Pharmaceuticals, Inc.

SY-1425-301

Response Criteria ^a		Peripheral	Blood		BMB (%)	Other
Crueriu	Hemoglobin	Neutrophils	Platelets	Blasts		
	(g/dL)	per (L)	per (L)	(%)		
PR					Decreased by ≥50% from baseline, but >5%	All CR criteria if abnormal before treatment except BMB
mCR	If HI response, note in addition to mCR				Decreased by \geq 50% from baseline, and \leq 5%	
Stable disease						Failure to achieve PR and no evidence of progression for >8 weeks
Failure						Death during treatment, or disease progression: worsening cytopenia, increase in % BMBs, progression to a more advanced MDS FAB subtype
Relapse after CR or PR						At least one of the following: Return to pretreatment BMB %. Decrement of ≥50% from maximum remission/response levels in granulocytes or platelets. Reduction in Hgb ≥1.5g/dL or transfusion dependence.
Cytogenet	Cytogenetic Response			1	1	1
Complete Partial			Disappearance of chromosomal abnormality with no appearance of new ones. ≥50% reduction of chromosomal abnormality			

Response Criteriaª		Peripheral Blood			BMB (%)	Other	
	Hemoglobin	Neutrophils	Platelets	Blasts			
	(g/dL)	per (L)	per (L)	(%)			
Disease Progression, participants with:		Evaluation C	Evaluation Criteria:				
<5% bone marrow blasts		\geq 50% increase to >5% bone marrow blasts					
5%-<10% l	bone marrow bla	sts	\geq 50% increase to >10% bone marrow blasts				
10%-<20%	0% -<20% bone marrow blasts \geq 50% increase t			e to ≥20%	bone marrow b	lasts	
For all categories			At least 50% decrease from maximum remission/response in granulocytes or platelets				
			or reduction in Hgb by ≥ 2 g/dL or transfusion dependence				

Abbreviations: BMB = bone marrow blasts; CR = complete remission; FAB = French-American-British; HI = hematologic improvement; Hgb = hemoglobin; IWG = International Working Group; mCR = marrow CR; MDS = myelodysplastic syndrome; PR = partial remission ^a Response must last at least 4 weeks.

The IWG criteria for HI define specific responses of cytopenias in the 3 hematopoietic lineages: erythroid (HI-E), platelet (HI-P), and neutrophil (HI-N). The HIs are measured in participants with pretreatment abnormal values: hemoglobin level less than 110 g/L (11 g/dL) or RBC-transfusion dependence, platelet count less than 100×10^9 /L or platelet-transfusion dependence, and absolute neutrophil count (ANC) less than 1.0×10^9 /L.

Table 8 Response Criteria for Hematologic Improvement for MDS

Hematologic Improvement	Response Criteria (Response Lasting 8 Weeks)
Erythroid response (pretreatment <11 g/dL)	Hgb increase by $\geq 1.5 \text{ g/dL}$
	Relevant reduction of units of RBC transfusions by an absolute
	number of at least 4 RBC transfusions/8 weeks compared with
	the pretreatment transfusion number in the previous 8 weeks.
	Only RBC transfusions given for a Hgb of $\leq 9.0 \text{ g/dL}$
	pretreatment will count in the RBC transfusion response
	evaluation.
Platelet response (pretreatment $<100 \times 10^{9}/L$)	Absolute increase of $\geq 30 \times 10^{9}$ /L if starting with $\geq 20 \times 10^{9}$ /L
	platelets
	Increase from $<20 \times 10^{9}/L$ to $>20 \times 10^{9}/L$ and by at least 100%
Neutrophil response (pretreatment $< 1 \times 10^{9}/L$)	At least a 100% increase and an absolute increase $>0.5 \times 10^9/L$
Progression or relapse after HI in the absence of	At least one of the following:
another explanation	At least 50% decrease from maximum response levels in
	granulocytes or platelets;
	Reduction in Hgb by ≥ 1.5 g/dL;
	Transfusion dependence.

Abbreviations: Hgb = hemoglobin; HI = hematologic improvement; MDS = myelodysplastic syndrome; RBC = red blood cell

Adapted from: Cheson 2006.

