- (e) Patients who have not progressed/relapsed will enter the Disease Follow-up period. Visits should occur every 3 months for response assessment until disease progression/relapse, death, or the occurrence of the expected number of OS events to support the final OS analysis, whichever occurs first. Disease Follow-up Visit window is ±14 days.
- (f) Patients who progress/relapse will be followed to document the start of subsequent anticancer therapy, the date of disease progression/relapse, the date of transformation to AML, and OS status by telephone (or another appropriate method) until the expected number of OS events to support the final OS analysis is observed. Survival Follow-up Visit contact window is ±14 days.
- (g) C1D1 assessments must be performed prior to study drug administration.
- (h) Cycles 2 through 4 only.
- (i) Eligibility review and approval by Sponsor or designee (via Eligibility Approval Form) must be completed prior to randomization.
- (j) Patients can be randomized earlier than C1D1, but within 72 hours of the first dose of study drug, to accommodate operational needs.
- (k) For all randomized patients, any untoward medical occurrences that happen before the first dose of the study drug should be captured as a part of medical history.
- (l) If administration of the 6th and 7th doses of azacitidine of the cycle is delayed to Days 8 and 9 (see footnote (dd)), the vital sign evaluation will shift from Days 6 and 7 to Days 8 and 9 to parallel azacitidine administration. C1D8 vital sign evaluation is required for all patients.
- (m) Definitions for the "full" and "abbreviated" physical examination are provided in Section 8.2.3; both must include an assessment for the presence of extramedullary AML.
- (n) Abbreviated physical examination will be performed at C1D8, C1D22, D1 of Cycles 2+, and at each Disease Follow-up Visit (see Section 8.2.3).
- (o) Laboratory assessments will be performed locally.
- (p) Screening hematology parameter evaluation must be performed prior to or at least 7 days following any blood product transfusion.
- (q) Additional unscheduled hematology evaluations may be performed up to 2 weeks after the bone marrow aspiration, for those patients in marrow CR without full peripheral blood count recovery at the time of the bone marrow aspirate, to assess whether they meet IWG criteria for CR.
- (r) See Section 10.2 for details.

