5.4 Exploratory Study Objectives

The exploratory objectives of this study are to:

- characterize and compare the cytogenetic CR rate of tamibarotene plus azacitidine vs placebo plus azacitidine,
- characterize and compare the molecular response rate of tamibarotene plus azacitidine vs placebo plus azacitidine,
- characterize and compare the change in transfusion requirements of tamibarotene plus azacitidine vs placebo plus azacitidine,
- characterize and compare the rate of consolidation treatment with allogeneic hematopoietic stem cell transplantation (HSCT) following treatment with tamibarotene plus azacitidine vs placebo plus azacitidine,
- characterize the pharmacokinetics (PK) of tamibarotene, and
- characterize myelodysplastic syndrome (MDS) molecular features associated with response and with loss of response for tamibarotene plus azacitidine vs placebo plus azacitidine.

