6 INVESTIGATIONAL PLAN

6.1 Overall Study Design

This is a Phase 3, multi-center, randomized, double-blind, placebo-controlled study comparing the activity of tamibarotene plus azacitidine to placebo plus azacitidine as first-line therapy in retinoic acid receptor alpha (RARA)-positive participants with newly diagnosed higher-risk MDS (HR-MDS). Enrollment in countries in North America, Europe, and Israel is planned.

At the Pre-screening Visit, blood samples will be collected and sent to the Almac Diagnostics Laboratory for assessment of RARA biomarker to determine study eligibility. Pre-screening assessments for the RARA biomarker will be performed within 45 days of Cycle 1 Day 1, and screening assessments for all other eligibility criteria will be performed within 30 days of Cycle 1 Day 1.

Approximately CCI HR-MDS participants will be screened, with approximately participants randomized in the study. Participants will be randomized 2:1 to receive either tamibarotene plus azacitidine or placebo plus azacitidine. Randomization will be stratified by the Revised International Prognostic Scoring System (IPSS-R) risk group (Intermediate, High, and Very High Risk) and by geographical region (North America, Western Europe, plus Israel, and Eastern Europe).

Response will be assessed by the investigator per the modified International Working Group (IWG) MDS criteria (Cheson 2006). Bone marrow aspirates will be collected to measure response on Day 1 of Cycles 2 and 4, followed by every third cycle (7, 10, 13, etc.), with bone marrow aspirates collected at other times as clinically determined based upon clinical findings or changes in peripheral blood counts. Following the response assessment on Day 1 of Cycle 7, those in CR may have the frequency of bone marrow aspirates for response assessment reduced to every 6 cycles.

Participants will undergo response and safety evaluations throughout their study participation as detailed in the protocol Schedule of Activities (Section 1.3 in the study protocol). Participants may continue to receive study drug until experiencing an unacceptable toxicity, disease progression (including transformation into acute myeloid leukemia [AML]), relapse, decision to pursue post-remission therapy (such as HSCT) or an alternative anticancer therapy, participant withdraws consent, or the investigator determines it is in the best interest of the participant to discontinue study drug.

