An End of Treatment (EoT) Visit should occur within 3 days of the last dose of study drug (or within 3 days of decision to permanently stop drug treatment, if this decision directly follows a period when study drug has been on hold) and before the start of any subsequent anticancer therapy. A Safety Follow-up Visit should occur 30 days (±3 days) after the EoT Visit and if possible before the start of any subsequent anticancer therapy. After the EoT Visit, participants who have not progressed/relapsed will enter the Disease Follow-up period, during which response assessments will be performed for up to 5 years after discontinuation of study drug (irrespective of initiation of HSCT or other subsequent anticancer therapy) or until disease progression/relapse, death, or the occurrence of the expected number of OS events to support the final OS analysis, whichever occurs first. It is estimated that a final analysis of OS will occur approximately 70 months following the enrollment of the first participant.

Participants who progress/relapse will enter Survival Follow-up and will be followed to document the start of subsequent anticancer therapy, the date of transformation to AML, the date of death, and OS status until the expected number of OS events to support the final OS analysis is observed.

An Independent Data Monitoring Committee (IDMC) will be established and will review the data at the 2 planned interim futility analyses and the safety interims, as specified in the IDMC Charter.

Figure 1 Study Design

Abbreviations: MDS = myelodysplastic syndrome; RARA = retinoic acid receptor alpha

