6.4 Efficacy and Safety Endpoints

Unless otherwise specified, all efficacy and safety endpoints will use participants' all available data up to the data cut-off.

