7.4.6.4 Consolidation with Allogeneic HSCT Rate

The number and percentage of participants treated and not treated with allogeneic HSCT, along with 95% exact binomial CIs based on Clopper-Pearson exact method, will be summarized by treatment group for the mITT Analysis Set.

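### The exploratory consolidation HSCT rate counts every allogeneic transplant, including those after non-response, relapse, AML transformation or other therapy, so it does not measure consolidation

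*SAP*

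**What the plan says.** SAP 6.4.1.4 defines the endpoint: "The rate of consolidation with allogeneic HSCT is defined as the proportion of participants who are treated with allogeneic HSCT". Its formula is "number of participants treated with allogeneic HSCT / number of participants in the mITT analysis set", times 100, per treatment group. Protocol Section 3 has the same definition. SAP 7.4.6.4 plans to summarize "The number and percentage of participants treated and not treated with allogeneic HSCT", with exact confidence intervals by arm. It specifies no between-arm test and no split by disease status.

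The data window is the default in SAP 6.4: "all efficacy and safety endpoints will use participants' all available data up to the data cut-off". Transplants after treatment failure fall inside it:

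- Protocol 1.3, footnote (x), has subsequent anticancer therapies, allogeneic HSCT among them, recorded after End of Treatment.
- Footnote (f) continues this after failure: "Patients who progress/relapse will be followed to document the start of subsequent anticancer therapy". SAP 6.1 agrees: "Participants who progress/relapse will enter Survival Follow-up and will be followed to document the start of subsequent anticancer therapy".

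Elsewhere the documents use transplant in a narrower sense. Among the reasons to stop study drug, SAP 6.1 lists "decision to pursue post-remission therapy (such as HSCT) or an alternative anticancer therapy", which sets transplant as post-remission therapy apart from other anticancer therapy. Protocol 7.1 makes the same distinction and, in the same bullet, permits consolidation with HSCT. The exploratory objective in SAP 5.4 is to compare the arms on consolidation transplant.

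**The concern.** Consolidation means treating a patient whose disease has responded. The formula also counts three other kinds of transplant: in a participant who never responded, in a responder who has since relapsed, progressed or transformed to AML, and in a participant who first received another anticancer therapy. No other section of either document removes these from the numerator.

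Such cases are plausible under the protocol. Section 7.1 stops study drug in patients without at least hematologic improvement after the Cycle 7 Day 1 assessment. Exclusion criterion 1 removes only patients who are both suitable for transplant and agree to it at screening. A patient who was suitable but declined can enroll and be transplanted later, after failure.

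At stake is what the study report says about transplant. A reader who sees a consolidation rate by arm will take it as the share of patients whom study treatment brought to transplant in response. The table as planned would show something else.

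**Working it through.** The documents state no HSCT rate, so there is no figure to reproduce. The check has two parts.

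**1. Does any rule limit the numerator?** SAP 6.4.1.4, 7.4.6.4 and 6.4 and Protocol Section 3 contain none. The SAP does draw the distinction for other endpoints. Situation 6 in Tables 13 and 14 identifies HSCT started before documented progression, relapse or death, and the transfusion-independence window ends when post-treatment therapy starts.

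**2. What does this do to the arm comparison?** For each arm let

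- p = response rate (pT for tamibarotene, pC for placebo);
- c = probability that a responder is transplanted while in response;
- r = probability that a responder is first transplanted only after relapse or other loss of response;
- s = probability that a non-responder is transplanted.

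Take c, r and s as equal in both arms.

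- Counted rate = p(c + r) + (1 − p)s
- True consolidation rate = pc
- Counted difference = (pT − pC)(c + r − s)
- True difference = (pT − pC)c
- Bias = (pT − pC)(r − s)

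If pT > pC, the counted difference is too small when s > r, right when s = r and too large when r > s. It is zero when s = c + r and reverses when s > c + r.

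Illustration (all values assumed): p = 50% vs 30% and c = 20%. True consolidation is 10% vs 6%, +4 points.

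| r | s | Counted, tamibarotene vs placebo | Difference (points) |
|---|---|---|---|
| 0 | 10% | 15% vs 13% | +2 |
| 10% | 10% | 20% vs 16% | +4 |
| 10% | 0 | 15% vs 9% | +6 |
| 0 | 20% | 20% vs 20% | 0 |
| 0 | 30% | 25% vs 27% | −2 |

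Example, second row: 0.5 × 0.30 + 0.5 × 0.10 = 0.20 and 0.3 × 0.30 + 0.7 × 0.10 = 0.16.

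The assumed CR rates are redacted. The one visible figure for a CR difference at the final analysis is the critical difference of 0.1349 in SAP Table 16. Take it as pT − pC, with CR as the only qualifying response and c = 20% (assumed):

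- True difference: 0.1349 × 0.20 = +2.7 points.
- r = 0, s = 10%: 0.1349 × 0.10 = +1.35 points.
- r = 10%, s = 10%: +2.7 points.
- r = 10%, s = 0: 0.1349 × 0.30 = +4.05 points.

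For c between 10% and 30% the true difference runs from +1.35 to +4.05 points.

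In counts, take 190 participants (the number in Protocol 9.4.2; the mITT size in the SAP is redacted) split 127:63, and suppose 13 vs 3 transplants in response: 10.2% vs 4.8%, +5.5 points.

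- Adding 4 vs 6 other transplants gives 17/127 = 13.4% vs 9/63 = 14.3%, −0.9 points. The exact 95% intervals are 8.0–20.6% and 6.7–25.4%.
- Adding 8 vs 2 instead gives 21/127 = 16.5% vs 5/63 = 7.9%, +8.6 points.

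A handful of patients can move the result either way, and the intervals are wide in any case.

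**The case against.** The share of participants receiving any allogeneic transplant is a well-defined quantity, and its formula is stated openly. The endpoint is exploratory, and its own section plans only counts, percentages and intervals. Usage is also mixed: the objective speaks only of transplant following study treatment, and the OS estimand groups HSCT with other subsequent therapy. Post-treatment therapies are summarized and listed (SAP 7.3.6) and response assessments are listed (SAP 7.4.1), so the split could be recovered afterwards.

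This lowers the priority but does not remove the point. The objective and the label both say consolidation, the stopping criteria in both documents call transplant post-remission therapy, and no consolidation rate under that meaning is pre-specified. The objective also asks for a comparison.

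A reader might go further and infer that the rule works against the arm with more remissions, so that its advantage shrinks, vanishes or reverses. The documents do not support that. It looks only at transplants in non-responders and ignores responders transplanted after relapse, who are counted too and push the other way. Reversal with equal propensities needs s > c + r, and nothing in the documents speaks to those values.

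**Conclusion.** The point stands as a misclassification. As written, transplants after failure of study treatment, or after other therapy, are reported as consolidation, which is not what the objective asks for. This rests on the text alone.

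The effect on the arm comparison has no known direction or size. With equal propensities the bias is (pT − pC)(r − s); with unequal propensities it depends on the arm-specific counts. The percentages above are illustrations under assumed rates, not estimates for this trial.

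The point is minor. The endpoint is exploratory and outside the alpha hierarchy, and the primary CR analysis, OS and the sample size are untouched.

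**What to change.** In SAP 6.4.1.4 and 7.4.6.4, and in the Protocol Section 3 endpoint, report three rows by arm, each over all mITT participants:

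1. **Consolidation HSCT**: a first allogeneic HSCT after randomization that follows a documented response on study treatment and precedes any documented relapse, progression, AML transformation or other subsequent anticancer therapy. Transplant conditioning does not count as other therapy. State which IWG categories qualify; whether hematologic improvement alone is enough is for the sponsor to decide in advance.
2. **Other allogeneic HSCT**: every other participant with an allogeneic transplant.
3. **Any allogeneic HSCT**: the total, which is the quantity now defined.

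The conditions on study treatment and intervening therapy are both needed. Response assessments continue in Disease Follow-up whatever therapy is started, so a response to a later therapy could otherwise qualify.

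The change is to analysis only and does not affect when a patient may be transplanted. It costs SAP wording, a matching protocol edit and simple programming. The response, progression, AML-transformation and subsequent-therapy data are already collected. SAP 7.1.3.5 has rules for partial start dates of later therapy, which can be extended to this endpoint.
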